2.2. Primary Objectives

To determine the effect of methadone on the duration on mechanical ventilation in critically ill patients receiving more than 72 hours of MV by comparing the number of ventilator free days form enrolment to the time of discharge

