2.3. Secondary Objectives

To assess the safety of methadone administration in critically ill patients while in the hospital.

To determine hospital length of stay from the time of enrollment to the time of discharge

2.4. Potential Risks and Benefits:

a. End Points – Efficacy

The study might show the efficacy and potency of methadone in decreasing the length of stay in ICU and duration of mechanically intubation in critically ill patients.

b. End Points - Safety

Adverse events that could be anticipated during the study include signs of opioid withdrawal, elevated liver enzymes, ileus, hypotension and QTC prolongation. Adverse events will be reported in the adverse events registry.

The only two adult studies reported on the use of methadone to wean opioids on mechanical ventilation showed that the much-anticipated risk of QTC prolongation was similar in both patients who received methadone and those that did not receive methadone as shown in the study by Wanzuita et al and Al-Qadheeb et al. [5] Methadone was well tolerated in both studies.

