2.5 Outcomes

a. Primary

Proportion of patients on methadone that get extubated by day number 5 from the date of intubation

b. Secondary

Proportion of patients that develop prolonged QTC after administration of methadone. Others will be ICU length of stay, ICU mortality, hospital length of stay and hospital mortality.

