4.2 Interventions

Pre-intervention period (1 month)

The objective of this period is to standardize the process to improve familiarity to the investigators. Study procedures will be presented to the nurses by oral presentations, printed material, and by email. The information will include detailed explanation of the process of tapering methadone and weaning patients off opiates as stipulated in the study. It will also elaborate more on the process of managing patients that develop clinical opiate withdrawal symptoms.

Intervention period

Following randomization patients will be assigned to the MG or the NG group. For patients randomized to the MG a "non-formulary medication" order will be placed in the electronic medical record to alert nurses to follow the protocol for patients started on Methadone. For those in the NG group usual hospital protocol of weaning opioids will be followed.

The study is completed for each patient once extubated or discharged from ICU, death, comfort care measures, or after 30 days of participation in the study.

We will collect data regarding participants demographic characteristics, comorbidities, main admission diagnosis, use of mechanical ventilation and vasopressors, ICU and hospital LOS, ICU and hospital mortality. Vital signs, focused general examination, LFTs, with normal ICU standard of care will done. However, EKG will be done at baseline and on day 30 if patient is still on methadone. LFTs are only done at baseline. The duration of use of the medication is not expected to cause an increase in LFTs. The listed labs are the only additional labs other than what is usually ordered for standard care in ICU. The information will be collected by reviewing medical records and will be recorded in electronic form only, using REDCap.

#UTHealth Houston

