6. METHODS AND ASSESSMENTS

Based on the assumptions of successful extubation by day 5 of 50% of patients in the methadone group and 20% of patients in the control group and using a two tailed alpha level of 5%, a power of 80% our sample size calculation comparing proportions of two groups yielded 76. A 5% fallout as correction factor was 4 leaving us with a sample size of 80 patients. Statistical methods will include descriptive statistics and time to event analysis. Baseline characteristics will be reported. Data will be collected on a data collection sheet prior to transfer to REDCAPs database (Appendix 6). We will generate Kaplan-Meier curves and for comparison of hazard between groups we will use Cox regression (Cox proportional hazards model). Patients who die will be censored at time of death. Time of weaning will take into consideration only patients who were permanently disconnected from the ventilator. QTc values will be obtained from patient monitors and documented on data collection tool daily.

Randomization tables will be generated using REDCAPs database by study statistician. At the end of the study recorded information from REDCAPs will be exported to STATA for statistical analysis.

#UTHealth Houston

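### If the planned time-to-event curves describe extubation, censoring deaths makes them overstate the share extubated; a raw length-of-stay comparison also counts an early death as a short stay.

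*Combined protocol and SAP*

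**What the plan says.** Section 6 (Methods and Assessments) sets out the time-to-event analysis: "We will generate Kaplan-Meier curves and for comparison of hazard between groups we will use Cox regression". Its rule for deaths is: "Patients who die will be censored at time of death". The next sentence reads: "Time of weaning will take into consideration only patients who were permanently disconnected from the ventilator". The event is never named. It cannot be death, since deaths are censored, and the neighbouring sentence is about weaning, so extubation is the evident reading. No section mentions cumulative incidence or any other competing-event method.

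Three other outcomes depend on how deaths are handled.

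- **Ventilator-free days.** Section 2.2 states the primary objective as "comparing the number of ventilator free days form enrolment to the time of discharge". It gives no fixed window and no score for a patient who dies.
- **Length of stay.** Section 2.3 has "To determine hospital length of stay from the time of enrollment to the time of discharge", and section 2.5 adds "Others will be ICU length of stay, ICU mortality, hospital length of stay and hospital mortality". Neither says how deaths enter. The only test that section 10.2 names for continuous variables is the t-test.
- **Day-5 primary outcome.** Section 2.5 makes this a proportion extubated, with no explicit rule for a patient who dies before day 5.

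On follow-up, section 4.2 says "The study is completed for each patient once extubated or discharged from ICU, death, comfort care measures, or after 30 days", and its list of data to collect includes "ICU and hospital LOS, ICU and hospital mortality".

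**The concern.** Kaplan-Meier treats a censored patient as someone who could still have the event later. That is reasonable for a patient lost to view, but not for one who has died on the ventilator. One minus Kaplan-Meier is therefore never below the true share extubated, and exceeds it once any extubation follows a death. Deaths are foreseeable here: the plan lists ICU and hospital mortality as outcomes and makes death one way in which participation ends.

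The sentence about permanent disconnection adds an ambiguity. It may only define the weaning event. Read literally, it restricts the analysis to patients selected by what happened after randomisation and leaves out those who died on the ventilator. That would be a different treatment of deaths from the censoring rule in the same paragraph.

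Length of stay fails in another way. In a t-test on raw days, a patient who dies early contributes a short stay, which looks like a good result. The censoring rule does not help, because it belongs to the curves and the Cox model.

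At stake is how the supporting efficacy results are read: extubation curves that sit too high, and length-of-stay differences that may partly reflect deaths.

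**Working it through.** **The plan's own figure.** Sections 6 and 10.1 assume extubation by day 5 of 50% against 20%, two-sided 5% alpha and 80% power, and give 76 patients, raised to 80. The arcsine formula is n per arm = 2(1.960 + 0.842)²/h², with h = 2·asin√0.5 − 2·asin√0.2 = 0.6435. This gives 37.9, so 38 per arm and 76 in total; 76/0.95 = 80. The figure reproduces. It rests on two proportions, so nothing below changes it.

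**Inputs.** The 20% and 50% rates come from the plan. Eligibility requires more than 72 hours of ventilation (section 3.3) and day 5 counts from intubation (section 2.5), so about 2 days is the most that can remain; 1 day is also shown. Assumptions: constant hazards carried to day 30, deaths only on the ventilator, no reintubation, and death hazards d of 0.005, 0.015, 0.030 and 0.045 per day.

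**Formulas.** With p the day-5 rate and r the days remaining:

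- extubation hazard e = −ln(1 − p)/r
- true share extubated by time T = e/(e + d) × [1 − exp(−(e + d)T)]
- deaths on the ventilator = d/(e + d) × [1 − exp(−(e + d)T)]
- one minus Kaplan-Meier = 1 − exp(−eT)

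**Control arm at day 30.** For p = 0.20, e = 0.1116 with 2 days remaining and 0.2231 with 1 day.

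| d | Deaths (2 days) | True extubated | 1 − KM | Gap | Deaths (1 day) | True extubated | 1 − KM | Gap |
|---|---|---|---|---|---|---|---|---|
| 0.005 | 4.2% | 92.8% | 96.5% | 3.7 | 2.2% | 97.7% | 99.9% | 2.2 |
| 0.015 | 11.6% | 86.2% | 96.5% | 10.3 | 6.3% | 93.6% | 99.9% | 6.3 |
| 0.030 | 20.9% | 77.7% | 96.5% | 18.8 | 11.8% | 88.1% | 99.9% | 11.8 |
| 0.045 | 28.5% | 70.6% | 96.5% | 25.9 | 16.8% | 83.2% | 99.9% | 16.7 |

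**Methadone arm at day 30.** For p = 0.50 and 2 days remaining, e = 0.3466. True extubation is 98.6%, 95.8%, 92.0% and 88.5%, against about 100% on the curve.

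**At day 5** (T = r = 2): the gap is 0.1 to 0.8 points at the control rate and 0.2 to 1.9 points at the methadone rate. With 1 day remaining it is smaller.

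**Between arms.** The direction depends on what is assumed.

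- *Equal extubation hazard (0.1116), death hazards 0.015 against 0.030.* True 30-day extubation is 86% against 78%, yet both curves reach 96.5%. The cause-specific ratio is 1.0; a simulated subdistribution ratio is about 0.84. The arm with more deaths looks better than it is, whichever arm that is.
- *The plan's two extubation rates with a common death hazard.* The true 30-day differences are about 6, 10, 14 and 18 points across the four death hazards. The Kaplan-Meier difference is 3.5 points throughout, so the curves understate the benefit of methadone.
- *True shares of 50% and 20%, with 20% dead in each arm by the same time.* Here 1 − KM = 1 − exp[ln(1 − p − q) × p/(p + q)], where q is the share dead. This gives 57.7% and 22.5%: a true 30-point gap reads as 35.2, so the benefit is overstated.

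**Length of stay.** Suppose a mean of 14 days in survivors and 5 days in those who die (illustrative values). With 20% mortality the mean is 0.8 × 14 + 0.2 × 5 = 12.2 days. With 40% it is 0.6 × 14 + 0.4 × 5 = 10.4 days. The mean falls by 1.8 days solely because more patients died.

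**The case against.** The strongest reply is that little of the main inference is touched. The primary outcome and the sample size rest on a day-5 proportion, where the gap is under 2 points in these scenarios. The Cox model with deaths censored gives a valid cause-specific ratio. Mortality is reported as an outcome in its own right, so a difference in deaths would be visible beside the curves. All of this stands.

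The large day-30 gaps also rest on assumptions. They carry a hazard inferred from 1 or 2 days unchanged to day 30, and they use death rates that the documents do not give. Eligibility requires reversal of the cause of respiratory failure, adequate oxygenation and haemodynamic stability, so the upper death rates may not occur. That stands too, which is why a range is shown. It does not remove the overstatement, which has the same sign at any death rate above zero.

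A reader might infer that censoring deaths tilts the comparison towards methadone, or hides harm. The documents do not support this: the working gives cases in both directions.

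A reader might also infer from Appendix 6, which lists durations rather than dates of extubation or death, that the data for a better analysis are missing. That does not follow. The table is broken in the text available, and section 4.2 says data come from chart review into REDCap.

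Lastly, ventilator-free days appear in the objective but not among the outcomes, and a 30-day version needs more than section 4.2 provides for, because participation ends at extubation. This is a fair limit on the remedy and is carried into it. How comfort care and patients leaving the ICU still ventilated enter the analysis is missing detail rather than an error.

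**Conclusion.** The point holds in a limited form. If the curves are of extubation, which is evident but not stated, one minus Kaplan-Meier with deaths censored overstates the share extubated. Under constant hazards, the control-arm excess at day 30 is about 4 to 26 points with 2 days remaining to day 5 (deaths of about 4% to 28%), or about 2 to 17 points with 1 day remaining (deaths of about 2% to 17%). These are scenario ranges, not predictions. At day 5 the excess is under 2 points.

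It would go too far to say that the Cox analysis is wrong, that the primary analysis is invalid, or that the bias favours methadone. The Cox ratio answers a cause-specific question and should not be read as a comparison of the chance of being extubated. The day-5 primary is little affected provided deaths count as not extubated, a rule the plan should state.

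The length-of-stay point stands separately: with no rule for deaths and a t-test as the only named method, early death shortens the measured stay. The change should be made before outcomes are seen, but the risk is misreading of supporting results, not failure of the primary one.

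**What to change.** In the statistical section:

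- Name the event. In all randomised patients, replace the Kaplan-Meier curves with the cumulative incidence of extubation to day 30, with death as a competing event.
- Keep the Cox ratio and label it cause-specific. A subdistribution ratio beside it is optional.
- Reword the sentence on permanent disconnection as the definition of the weaning event, not a restriction of the population.
- State that a death before day 5 counts as not extubated in the primary outcome.
- Analyse ICU and hospital length of stay as time to discharge alive, with death competing.
- If ventilator-free days are kept, define them over a fixed window with deaths scored 0. Do this only if ventilation status, reintubation and death after extubation can be obtained by chart review, since section 4.2 ends participation at extubation.

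The cost is SAP wording and a few lines in Stata, the package the plan already names. It needs no extra patients and no change to treatment. The small downside is that dates of extubation, reintubation, discharge and death must be confirmed in REDCap, or added if they are not there.

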2. HYPOTHESIS AND OBJECTIVES

2.1. Hypothesis

The study hypothesizes that patients who get oral methadone to help wean off opioids will have shorter ICU length of stay, shorter duration on the ventilator and potentially improved hospital mortality. The study hypothesizes that, there will be increase in the proportion of patients extubated by day 5.

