10.2. Statistical and Analytical Plans

Methadone when used at appropriate doses is considered safe and is an FDA approved medication. We will not be performing safety analysis. We will perform interim analysis after randomizing up to 50%(40) patients. Categorial variable will be compared using the student Chisquared test and continuous variables will be compared using the T-test. Interim analysis will be performed by an independent statistician blinded for the treatment allocation. The statistician will report to the data safety and monitoring committee. The DSMB will discuss the results of the interim analysis with the statistician and a steering committee and in a joint meeting will decide on continuation of the trial.

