Bone or Joint aches If patient was having pain previously, only the additional component attributed to opiates withdrawal is scored O not present mild diffuse discomfort patient reports severe diffuse aching of joints/muscles patient is rubbing joints or muscles and is unable to sit still because of discomfort	Gooseflesh skin 0 skin is smooth 3 piloerrection of skin can be felt or hairs standing up on arms 5 prominent piloerrection			
Runny nose or tearing Not accounted for by cold symptoms or allergies 0 not present 1 nasal stuffiness or unusually moist eyes 2 nose running or tearing 4 nose constantly running or tears streaming down cheeks	Total Score The total score is the sum of all 11 items Initials of person completing assessment:			

Score: 5-12 = mild; 13-24 = moderate; 25-36 = moderately severe; more than 36 = severe withdrawal This version may be copied and used clinically.

Journal of Psychoactive Drugs

[figure not shown]
Volume 35 (2), April - June 2003

Source: Wesson, D. R., & Ling, W. (2003). The Clinical Opiate Withdrawal Scale (COWS). J Psychoactive Drugs, 35(2), 253–9.

Appendix 5

Protocol Flow

Appendix 6

#UTHealth Houston

Data Collection Tool

Patient Identification Code (MRN):

Baseline Characteristics Age (years) Sex		
Sex		
Race		
Weight (Kg)		
Duration on ventilator at time of		
randomization (Hours)		
	Pneumonia = 1	
, , ,	Aspiration = 2	
	Non-Pulmonary Sepsis = 3	
	COPD Exacerbation = 4	
	Other Causes = 5	
Assessments and Measurements	Other Causes - 5	
APACHE II Score		
Total SOFA Score		
Tidal Volume ml/kg of predicted		
body weight		
Peep at time of enrollment (cm H2O)		
PaO2: FIO2 ratio (mmHg)		
FiO2 at time of enrollment		
Duration on mechanical ventilation		
before start of weaning(hours)		
Last recorded Ph prior to enrollment		
Duration in ICU stay after enrollment		
(Hours)		
Mean QTc while on Methadone		
Clinical Opiate Withdrawal Scale		
(COWS) after extubation		
Adverse Event		
Medication Parameters		
Fentanyl Initial Dose (mcg/hour)		
Fentanyl accumulated dose(mcg)		
Days on Fentanyl before start of		
weaning		
Hydromorphone initial Dose		
(mg/hour)		
Hydromorphone accumulated		
dose(mg)		
Days on Hydromorphone before		
start of weaning		
Dexmedetomidine accumulated		
dose(mcg)		
Midazolam accumulated dose(mg)		
Propofol accumulated dose (mg)		
Ketamine accumulated dose (mg)

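### Limiting time of weaning to patients permanently disconnected from the ventilator, if followed as written, selects the analysis set on the outcome and clashes with the rule that censors deaths

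*Combined protocol and SAP*

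**What the plan says.** Section 6 plans descriptive statistics and a time-to-event analysis with Kaplan-Meier curves, and "for comparison of hazard between groups we will use Cox regression (Cox proportional hazards model"). It then gives two consecutive rules. The first is "Patients who die will be censored at time of death". The second is "Time of weaning will take into consideration only patients who were permanently disconnected from the ventilator".

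Section 10.2 adds that "continuous variables will be compared using the T-test". Section 4.2 ends a patient's participation at extubation, ICU discharge, death, comfort care or 30 days.

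Duration of ventilation matters to the trial's aims. Section 2.1 hypothesises "shorter ICU length of stay, shorter duration on the ventilator and potentially improved hospital mortality", and section 2.2 makes duration of ventilation the primary objective, measured by ventilator-free days. The primary outcome in section 2.5 is the proportion extubated by day 5. Time of weaning is not among the secondary outcomes listed there.

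The documents do not say whether the second rule governs the Cox model, a t-test or only a descriptive summary. They also name no time origin for the time-to-event analysis.

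**The concern.** The second rule is worded as a restriction on patients. Taken at its word, anyone who dies ventilated, leaves the ICU ventilated or is still ventilated at day 30 contributes no weaning time. Membership of the analysis set then depends on an outcome that treatment may change, and randomisation no longer protects the comparison.

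The plan's own hypotheses make unequal exclusion likely. If methadone changes mortality or the chance of extubation, the excluded share differs by arm. Entry requires failed spontaneous breathing trials (section 3.3), so patients who are never disconnected are to be expected.

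The two rules also do not fit together in one analysis. A set made up only of disconnected patients has no one who died on the ventilator to censor, so two analysts could build different datasets from the same paragraph. At stake is whether a shorter weaning time in one arm reflects faster weaning or only who was left to be counted.

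**Working it through.** **1. The plan's own figure.** The inputs in section 6 are "successful extubation by day 5 of 50% of patients in the methadone group and 20% of patients in the control group", two-sided 5% alpha and 80% power. By the arcsine method, h = 2·asin(√0.5) − 2·asin(√0.2) = 1.5708 − 0.9273 = 0.6435. Then n = 2·((1.960 + 0.842)/0.6435)² ≈ 37.9, so 38 per arm and 76 in total, as stated. The pooled normal formula gives 39 per arm, or 78. The 5% allowance gives 76/0.95 = 80. None of this uses weaning time.

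**2. More deaths look faster.** The documents give no death or weaning rates, so all rates below are assumptions. Take constant rates L (weaning) and D (death on the ventilator), r = L + D, and horizon T = 30 days from section 4.2.

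- Share weaned = (L/r)·(1 − e^(−rT))
- Share dead while ventilated = (D/r)·(1 − e^(−rT))
- Mean time among weaned = 1/r − T·e^(−rT)/(1 − e^(−rT))

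The weaned-only mean depends on r, not on L alone. With L = 0.08 per day in both arms:

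| D per day | Mean time among weaned (days) | Weaned | Dead while ventilated |
|---|---|---|---|
| 0.02 | 10 − 30×0.0498/0.9502 = 8.43 | 76% | 19% |
| 0.04 | 8.333 − 30×0.0273/0.9727 = 7.49 | 65% | 32% |
| 0.06 | 7.143 − 30×0.0150/0.9850 = 6.69 | 56% | 42% |

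The apparent gain is 8.43 − 7.49 = 0.94 days when the death rate doubles and 8.43 − 6.69 = 1.74 days when it triples. The weaning rate is the same throughout.

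**3. Range over the weaning rate.** Set L so that, without deaths, 20% are weaned in 2 days (L = −ln 0.8/2 = 0.112) or in 5 days (L = −ln 0.8/5 = 0.045). Raising D from 0.02 to 0.06 then moves the weaned-only mean from 7.0 to 5.7 days, or from 10.4 to 8.2 days.

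**4. Effect on the test.** Simulation with 40 per arm, 2,000 runs per scenario and equal weaning rates, so a valid test should reject in about 5%:

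| Scenario | Log-rank, weaned only | t-test, weaned only | Log-rank, all randomised, deaths censored |
|---|---|---|---|
| L = 0.112, D = 0.02 vs 0.06 | 15.3% | 13.3% | 5.4% |
| L = 0.045, D = 0.02 vs 0.06 | 16.7% | 13.4% | 5.3% |
| L = 0.045, D = 0.02 vs 0.04 | 9.0% | 8.4% | 5.6% |

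The arm with more deaths had the shorter weaned-only mean in about 81% of runs in the first two scenarios and 69% in the third.

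**5. Rescue can look slower.** Suppose 60% of patients wean at a mean of 6 days, and treatment adds a further 20% who wean at a mean of 15 days. The weaned-only mean rises from 6.0 to (0.6×6 + 0.2×15)/0.8 = 8.25 days although more patients are weaned.

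As a range, assume no deaths, 60% easy-to-wean patients unaffected by treatment, and 40% never weaned on control. Let treatment wean the hard group at 0.02, 0.05 or 0.1 per day. With the 2-day calibration the mean goes from 4.9 to 6.9, 7.1 or 6.3 days. With the 5-day calibration it goes from 9.4 to 10.5, 10.2 or 9.0 days. In the last case the mean falls, so this reversal is not universal.

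**The case against.** The strongest reply is that the sentence was never meant to define an analysis set. Censoring deaths makes sense only if unweaned patients are at risk. In that context the sentence may say that only permanent disconnection counts as the event, or it may describe a summary weaning time beside the Cox model. Under the event reading the Cox comparison does not select on the outcome, and step 4 shows the log-rank test near its nominal level. This stands as a plausible intention. It does not rescue the text, which restricts patients and not events, and the reader is not told which analysis it governs.

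A second reply is that the distortion would be visible. ICU and hospital mortality are separate secondary outcomes, and ventilator-free days are the stated measure for the primary objective. That is fair. It limits the harm but does not make the weaned-only comparison valid.

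A third is that the sizes are assumed and the largest needs a tripled death rate. That is also true. The direction in step 2 follows from the formula, but the size does not come from the trial.

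A reader might infer two further faults that the documents do not support:

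- **An arm-dependent time zero.** Appendix 6 mentions the start of weaning, but only within data fields. No section makes it the origin of any analysis, and the same sheet records ventilator time at randomisation. What is true is that no origin is stated.
- **Loss of everyone who fails an extubation.** Even on the literal reading, a patient who is reintubated and later permanently disconnected stays in.

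**Conclusion.** The concern holds for the text as written. Followed literally, the rule conditions the weaning-time comparison on a post-randomisation outcome and cannot be applied together with the censoring rule in one analysis. Under the assumed rates, equal weaning with a doubled or tripled death rate appears 0.9 to 1.7 days faster. With 40 per arm, tests on weaned patients reject a true null in about 8% to 17% of runs. These figures rest on constant, independent rates that the documents do not supply. The opposite distortion is real in some settings and absent in others.

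A reader might go on to conclude that the trial's primary result or its size is compromised. The documents do not support that. The day-5 proportion is not defined on weaned patients, and it alone sets the 80. The affected analysis is the Kaplan-Meier and Cox comparison, or any t-test, of weaning time. It should be corrected before analysis because it bears on a stated hypothesis and the correction is cheap.

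**What to change.** Replace the sentence in section 6 with:

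> All randomised patients enter the time-to-weaning analysis, with time measured from randomisation in both arms. Permanent disconnection defines the event, not the analysis set. Patients who die or are not disconnected remain in the risk set until death, last known ventilator status or day 30. Any time among weaned patients only is descriptive and is not compared between arms.

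Two things must go with it:

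- **Data.** The Appendix 6 sheet, as it appears in the document, has no field for date and time of final disconnection, or for ventilator status at death, ICU discharge or day 30. Both can come from the chart review already planned in section 4.2.
- **Reconciliation with section 4.2.** Participation ends there at extubation, ICU discharge or comfort care. The plan should say whether ventilator status is still read from the chart after those points, and over what stated period a disconnection is judged permanent.

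Whether death should be handled as a competing event is a separate question, and this change does not depend on it. Treatment, eligibility and sample size do not change.
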